6.3 Central Nervous System (CNS) Prophylaxis

Patients with a history of CNS involvement of leukemia, with monocytic differentiation, or with a WBC >40,000 cells/ μ L should receive a lumbar puncture using either intrathecal (IT) methotrexate or cytarabine, following site-specific standard operating procedures during the first induction cycle of CPX-351 with quizartinib.

The CNS prophylaxis regimen may be modified by the attending physician in consultation with the PI as clinically indicated. No further IT chemotherapy is required in this study if there is no evidence of disease. However, additional administrations, per the treating physician or per institutional standard operating procedures, are permitted.

In patients who have CNS disease involvement, IT chemotherapy should continue every 4 days (\pm 1 day) until disease clearance, followed by every 7 days (\pm 2 days) for 2 additional administrations. Thereafter, administer IT chemotherapy every 28 days (\pm 7 days) for at least 12 cycles.

6.4 Study Assessment Timing

The treatment period begins on the day the patient receives the first administration of CPX-351. Dates for study visits and assessments will be determined based upon the first day of treatment and should occur based on the timing parameters outlined in this protocol.

6.4.1 Induction Phase

- Serum pregnancy test once per cycle during the induction phase

6.4.1.1 Cycle 1, Days 1, 3 and 5

- Physical examination and vital signs (Days 3 and 5)
- ECOG performance status (Days 3 and 5)
- AE monitoring
- Concomitant medication review
- CBC and clinical chemistry panel
- CPX-351 administration (Days 1, 3, and 5)

6.4.1.2 Cycle 1, Day 8

- Physical examination and vital signs
- ECOG performance status
- AE monitoring
- Concomitant medication review
- CBC and clinical chemistry panel

CONFIDENTIAL

STUDY DRUG: QUIZARTINIB
PROTOCOL DATE: 10 AUGUST 2020

DEVELOPMENT INNOVATIONS STUDY NUMBER: AML 48
VERSION 4.0

- ECG and QTc assessment
- Quizartinib daily on Days 8-21 (if QTcF \leq 450 msec)

6.4.1.3 **Cycle 1 Day 14**

- Physical examination and vital signs
- ECOG performance status
- AE monitoring
- Concomitant medication review
- CBC and clinical chemistry panel
- ECG and QTc assessment (if QTcF >470 msec, see Appendix F)

6.4.1.4 **Cycle 1 Day 21 (Response assessment)**

- Physical examination and vital signs
- ECOG performance status
- AE monitoring
- Concomitant medication review
- CBC and clinical chemistry panel
- BM biopsy and aspirate with FLT3 mutation testing via PCR
- ECG

6.4.1.5 **Cycle 1 Day 35 (\pm 7 days) (BM recovery)**

- Physical examination and vital signs
- ECOG performance status
- AE monitoring
- Concomitant medication review
- CBC and clinical chemistry panel
- BM biopsy and aspirate for MRD assessment via next-generation sequencing (NGS) and FLT3 mutation testing via PCR

6.4.1.6 **Cycle 2, Days 1 and 3 (re-induction, only applicable if patient achieves PR with recovery bone marrow after Cycle 1)**

- Physical examination and vital signs (Days 3 and 5)
- ECOG performance status (Days 3 and 5)
- AE monitoring
- Concomitant medication review
- CBC and clinical chemistry panels

CONFIDENTIAL

- CPX-351 administration (Days 1 and 3)

6.4.1.7 Cycle 2, Day 6

- Physical examination and vital signs
- ECOG performance status
- AE monitoring
- Concomitant medication review
- CBC and clinical chemistry panels
- ECG and QTcF assessment (if QTcF \leq 470 msec, resume quizartinib)
- Quizartinib (daily on Days 6-21, if QTcF \leq 470 msec)

6.4.1.8 Cycle 2 Day 14

- Physical examination and vital signs
- ECOG performance status
- AE monitoring
- Concomitant medication review
- CBC and clinical chemistry panel
- ECG and QTc assessment (if QTcF $>$ 470 msec, see Appendix F)

6.4.1.9 Cycle 2 Day 21 (Response assessment)

- Physical examination and vital signs
- ECOG performance status
- AE monitoring
- Concomitant medication review
- CBC and clinical chemistry panel
- BM biopsy and aspirate with FLT3 mutation testing via PCR
- ECG

6.4.1.10 Cycle 2 Day 35 (\pm 7) (BM recovery)

- Physical examination and vital signs
- ECOG performance status
- AE monitoring
- Concomitant medication review

CONFIDENTIAL

- CBC and clinical chemistry panel
- BM biopsy and aspirate for MRD assessment via next-generation sequencing (NGS) and FLT3 mutation testing via PCR

6.4.2 Consolidation Phase (If applicable)

- Patients who achieve CR and do not receive an alloHCT or other CT intervention will receive up to 2 cycles of consolidation therapy with CPX-351 and quizartinib.
- Serum pregnancy test once per cycle during the consolidation phase

6.4.2.1 Cycle 1, Day 1 and 3

- Physical examination and vital signs
- ECOG performance status
- AE monitoring
- Concomitant medication review
- CBC and clinical chemistry panel
- CPX-351 (Days 1 and 3)
- ECG (Day 3)

6.4.2.2 Cycle 1, Day 6

- Physical examination and vital signs
- ECOG performance status
- AE monitoring
- Concomitant medication review
- CBC and clinical chemistry panel
- ECG and QTcF assessment (if QTcF \leq 470 msec, resume quizartinib on Day 4)
- Quizartinib (begin daily until Day 21)

6.4.2.3 Cycle 1 Days 14 and 21

- ECG

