Study Drug, Dose, and Mode of Administration:	
Induction phase: CPX-351 (daunorubicin 44 mg/m² IV and cytarabine 100 mg/m² IV) will be given on Days 1, 3, and 5 followed by 30 mg quizartinib by mouth (PO) once daily on Days 8-21. Patients with an incomplete response, but a >50% reduction in the blast count/cellularity ratio compared to the most recent bone marrow (BM) biopsy prior to treatment, should receive one additional cycle of induction therapy (re-induction) with CPX-351 (daunorubicin 44 mg/m² IV and cytarabine 100 mg/m² IV) on Days 1 and 3 only. Re-induction will begin after a 72-hour washout period from the last dose of quizartinib. During re-induction, treatment with quizartinib will resume on Day 6 and continue through Day 21. Any patient with neutropenia or thrombocytopenia lasting ≥ 56 days from the initiation of CPX-351 will not receive consolidation and will instead proceed to the maintenance phase.
 
Consolidation phase: At the Investigator's discretion, patients who achieve CR and do not proceed to an alloHCT or other CT intervention will proceed to the consolidation phase beginning 7 days (± 7) after neutrophil recovery (ANC >1000/μL). Administer up to 2 consolidation cycles of CPX-351 (daunorubicin 29 mg/m² IV and cytarabine 65 mg/m² IV) on Days 1 and 3. Begin quizartinib 30 mg PO once daily on Days 6-21.
 
Maintenance phase: Maintenance dosing of quizartinib will begin at 30 mg/day on Days 1-14, and if there are no non-hematologic Grade ≥ 3 toxicities, the quizartinib dose will increase to 60 mg/day on Day 15. The maintenance phase is a 28-day cycle beginning 7 days (± 7) after neutrophil recovery (ANC >1000/μL) from the consolidation phase or induction phase. Patients will receive quizartinib once daily for a total of 24 cycles or until disease relapse

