5.2.3 Consolidation Phase

Patients who achieve a CR and do not proceed to an alloHCT or other CT intervention will proceed from induction to the consolidation phase beginning 7 days (± 7 days) after neutrophil recovery (ANC $> 1000/\mu\text{L}$), receiving up to 2 consolidation cycles consisting of CPX-351 (daunorubicin 29 mg/m² IV and cytarabine 65 mg/m² IV) on Days 1 and 3. Quizartinib therapy (30 mg PO once daily) will start on Day 6 and continue through Day 21.

After the first consolidation cycle, if it is believed by the PI and/or sub-investigator that a patient with prolonged Grade ≥ 3 toxicity would have additional adverse toxicities during the second consolidation phase, and/or there is CRi with persistent ANC $< 1000/\mu\text{L}$ and/or platelets $< 50,000/\mu\text{L}$ more than 14 days from the recovery marrow assessment, then the patient could proceed to a cellular intervention or the maintenance phase.

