7.2 Quizartinib Treatment Duration

Patients will receive oral quizartinib once daily, on Days 8-21 of the induction cycle and Days 6-21 of re-induction, if necessary. Administration cannot begin earlier than 24 hours from the last administration of CPX-351. During the consolidation cycles(s), quizartinib begins on Day 6.

Prior to initiation (≤ 24 hour), ECGs in triplicate will be obtained to assess QTcF. If the QTcF is ≤ 450 msec, treatment with quizartinib may proceed (see Section 8). Patients proceeding to an additional cycle of induction as well as those proceeding to consolidation therapy must ensure the FLT3 inhibitor has not been administered before a 4-5 half-life reduction of quizartinib, equivalent to 3 days from the date of last administration.

CONFIDENTIAL

STUDY DRUG: QUIZARTINIB
 PROTOCOL DATE: 10 AUGUST 2020

DEVELOPMENT INNOVATIONS STUDY NUMBER: AML 48
 VERSION 4.0

After induction and consolidation cycles, patients will start maintenance therapy with quizartinib, continuing treatment on Days 1-28 of a 28-day cycle for a total of 24 maintenance cycles.

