Underlying disease assessment	X																		X ^m	
Survival status																			X ^m	

- a **Induction:** CPX-351 (daunorubicin 44 mg/m² IV and cytarabine 100 mg/m² IV) will be given IV on Days 1, 3, and 5 during induction therapy followed by quizartinib 30 mg orally (PO) once daily on Days 8-21 (hold quizartinib on Day 21). Patients with an incomplete response, but a >50% reduction in the blast count/cellularity ratio compared to the most recent BM biopsy prior to treatment, may receive one additional cycle of induction therapy (re-induction) with CPX-351 (daunorubicin 44 mg/m² IV and cytarabine 100 mg/m² IV) on Days 1 and 3 (see Section 5.2.2). During **re-induction**, begin CPX-351 at least 72 hours after the last dose of quizartinib. Treatment with quizartinib will resume on Day 6 and continue through Day 21 (hold quizartinib on Day 21, if proceeding to consolidation phase) (see Section 5.2.3).
- b **Consolidation:** Patients who achieve CR and do not proceed to an alloHCT or other CT intervention will proceed to the consolidation phase beginning 7 days (± 7 days) after neutrophil recovery (ANC >1000/μL). Administer up to 2 consolidation cycles of CPX-351 (daunorubicin 29 mg/m² IV and cytarabine 65 mg/m² IV) on Days 1 and 3. Begin quizartinib 30 mg PO once daily on Days 6-21 (hold quizartinib on Day 21) (see Section 5.2.3). Administration cannot begin earlier than 24 hours from the last administration of CPX-351 (see Section 7.2).
- c **The 60-day period (~Day 30) between the end of consolidation and the start of maintenance therapy.** Patients who proceed to alloHCT or other CT intervention after consolidation will resume quizartinib maintenance 30-60 days from the intervention. In patients who proceed to alloHCT, begin quizartinib maintenance no earlier than day 30 after transplant (see Section 5.2.4).

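### Section 6.4.2.2 tells sites to resume quizartinib on Day 4 although the deciding ECG and every other statement are at Day 6, and the Day 6 entries give no action above 470 msec

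*Combined protocol and SAP*

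**What the plan says.** **Start day in consolidation.** Section 6.4.2.2 is the Day 6 visit of consolidation Cycle 1. It lists an ECG and QTcF assessment and, for a reading at or below the limit, says "470 msec, resume quizartinib on Day 4". The next line of the same visit begins daily dosing to Day 21. Section 5.2.3 says quizartinib "will start on Day 6 and continue through Day 21". Section 7.2 says "During the consolidation cycles(s), quizartinib begins on Day 6". Appendix D footnote b says "Begin quizartinib 30 mg PO once daily on Days 6-21 (hold quizartinib on Day 21". The synopsis also gives Days 6-21. The matching entry for consolidation Cycle 2 (6.4.2.6) carries the same limit and no day number.

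**Spacing after CPX-351.** Section 7.2 also says "Administration cannot begin earlier than 24 hours from the last administration of CPX-351". The last consolidation dose of CPX-351 is on Day 3.

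**QTcF limit at Day 6.** Section 6.4.1.7 (re-induction) allows dosing at or below "470 msec, resume quizartinib" and repeats the condition on its dosing line: "daily on Days 6-21, if QTcF" is within the limit. Sections 6.4.2.2 and 6.4.2.6 use the same 470 msec limit. None of the three says what to do above it. The Day 14 induction entries and the maintenance entry do: they send readings above 470 msec to Appendix F.

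**Appendix F.** Grade 1 keeps the same dose. Grade 2 (above 480 msec) reduces the dose without interruption, or interrupts for up to 14 days if the patient is already on 20 mg. Grade 3 (above 500 msec) interrupts for up to 14 days.

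**The concern.** The Day 4 wording is an operative dosing instruction in the visit list that site staff work from. It cannot be reconciled with the visit that contains it, because a Day 6 ECG cannot authorise a dose two days earlier. A site that did start on Day 4 would have only the Day 3 ECG behind it, and 6.4.2.1 attaches no QTcF limit to that ECG.

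The silence above 470 msec is a separate weakness. The entry implies that the drug is not given, but it does not say so, and it does not say what happens next. Appendix F is the obvious place to look, and at some readings it leads to giving the drug.

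What is at stake is uniform conduct of a safety rule. The protocol describes QT prolongation with quizartinib as dose-dependent, makes it an adverse event of special interest (11.4), and reports it in 26.6% of quizartinib patients in the completed Phase 3 study, 4.1% at Grade 3 (7.5.1).

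**Working it through.** The plan states no dose count, so there is no figure to reproduce. The check has two parts.

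**1. Size of the Day 4 slip (consolidation Cycle 1 only)**

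Inputs: Day 4 from 6.4.2.2; Day 6 and last day 21 from 5.2.3; the Day 21 hold from Appendix D footnote b.

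Daily doses = last dosing day − first dosing day + 1.

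| First dose | Day 21 dosed | Day 21 held |
|---|---|---|
| Day 4 | 21 − 4 + 1 = 18 | 20 − 4 + 1 = 17 |
| Day 6 | 21 − 6 + 1 = 16 | 20 − 6 + 1 = 15 |
| Difference | 2 | 2 |

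The two extra doses fall on Days 4 and 5, before the Day 6 ECG. The gap from the last CPX-351 dose (Day 3) is 1 day instead of 3. One day still meets the 24-hour minimum in 7.2, so that rule alone would not catch the slip.

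**2. Action at a Day 6 visit by QTcF value**

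Inputs: the 470 msec limit from the three Day 6 entries; 480 and 500 msec from Appendix F. Appendix F gives no number for Grade 1; since Grade 2 starts above 480, readings of 471-480 are treated as Grade 1.

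| QTcF (msec) | Day 6 entries | Appendix F, on 30 mg | Appendix F, on 20 mg |
|---|---|---|---|
| 470 or less | restart | same dose | same dose |
| 471-480 | no restart (implied) | same dose | same dose |
| 481-500 | no restart (implied) | reduce, no interruption | interrupt up to 14 days |
| above 500 | no restart (implied) | interrupt up to 14 days | interrupt up to 14 days |

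The immediate action therefore differs over 471-500 msec for patients on 30 mg and only over 471-480 msec for patients on 20 mg. I leave the size of the Grade 2 reduction unstated: the QTcF column of the dose-modification table refers to 8.2.1, which names no dose level.

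Section 8.2.1 adds a review of electrolytes and co-medication and daily repeat ECGs for up to 3 days when QTcF exceeds 450 msec. It gives no rule if the reading stays high after that.

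A patient meets at most three such visits: one in re-induction and two in consolidation. That is a ceiling, because re-induction needs a PR, and consolidation needs a CR without transplant or other cellular therapy.

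**The case against.** **The Day 4 wording is a harmless typo.** Largely right. Four other places fix Day 6, and the visit's own heading and dosing line agree with them. A reader might infer from the 24-hour rule that nothing else in the protocol stops a Day 4 start. The documents do not support that: 5.2.3, 7.2, the synopsis and Appendix D all contradict it. What stands is that the visit instruction itself is wrong and should be corrected.

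**Appendix F does not apply at Day 6.** This is the stronger objection. Appendix F speaks of continuing, reducing and interrupting a current dose, so it addresses patients on drug. At Day 6 the patient is off drug: at least 72 hours before CPX-351 Day 1, plus 5 days to Day 6, makes about 8 days. The visits that point to Appendix F are on-treatment visits. A reader might infer two rival rules for one decision across 471-500 msec in every patient. That goes too far, both for this reason and because the 20 mg group differs only at 471-480. That group may not be small: strong CYP3A4 inhibitors require 20 mg (5.3.2), and voriconazole, listed as one in Appendix H, is named as routine prophylaxis (5.3.1). What remains is a missing action and a missing statement of which text governs.

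**Further conflicts a reader might infer.** After a QTcF interruption, Appendix F asks for 450 msec or less, or within 30 msec of baseline, against 470 at Day 6. For re-induction this is nearly empty. With the earliest recovery marrow (Day 28) and re-induction starting that day (an assumption), Day 6 is induction Day 33. Only an interruption begun on Days 19-21 is then still within 14 days. With a Day 35 marrow, Day 6 is induction Day 40 and none is. Timing for entry to consolidation was not worked out. Nor do I read the 450 msec limit in 7.2 as a third restart threshold: exclusion 8, 6.5.3 and the induction Day 8 entry tie it to the first dose.

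**Conclusion.** The Day 4 instruction in 6.4.2.2 is wrong as written. It is confined to consolidation Cycle 1 and, if followed, adds two doses before the deciding ECG (18 against 16, or 17 against 15 if Day 21 is held).

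Secondarily, the three Day 6 entries lack an action above 470 msec, and no text says whether they or Appendix F govern the first dose of a cycle. Reading no restart above 470 msec into those entries is an inference from their condition, though the natural one.

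Severity is minor. The documents do not allow an estimate of how many patients would reach a Day 6 visit with a reading in the affected range. No endpoint, analysis or sample size figure changes.

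**What to change.** 1. In 6.4.2.2, change Day 4 to Day 6.
2. In 6.4.1.7, 6.4.2.2 and 6.4.2.6, add that above 470 msec quizartinib is held, electrolytes and co-medications are corrected, and the ECG is repeated daily for up to 3 days. State that this start-of-cycle check, not the on-treatment steps of Appendix F, applies before the first dose of a cycle. The clinical team should set the action if QTcF stays above 470 msec, for example omitting quizartinib for that cycle.
3. Optional note: Appendix F gives no outcome if QTcF has not recovered within its 14 days, although it does for non-hematologic toxicity at 28 days. The general toxicity criterion in 3.3 covers this only in part.

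Leave the 450 msec sentence in 8.2.1 as it is. The repeat-ECG allowance follows from it, and restricting it to induction Day 8 would remove the support for step 2.

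The cost is amendment wording in three visit entries and, if wanted, one line in Appendix F. Scheduled visits and ECGs do not change. A patient who qualifies only on the third repeat day would start on Day 9 and receive 21 − 9 + 1 = 13 doses (12 if Day 21 is held), three fewer than planned.

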5.2.2 Induction Phase

Treatment consists of CPX-351 (liposomal daunorubicin $44 \text{ mg}/\text{m}^2$ IV and cytarabine $100 \text{ mg}/\text{m}^2$ IV) on Days 1, 3, and 5 followed by quizartinib (30 mg by mouth [PO] once daily) on Days 8-21. If there is a PR at the recovery BM biopsy, patients may be re-treated with one additional induction therapy (re-induction) with CPX-351 (daunorubicin $44 \text{ mg}/\text{m}^2$ IV and cytarabine 100

CONFIDENTIAL

mg/m² IV) on Days 1 and 3. Quizartinib (30 mg by PO once daily) will resume on Day 6 and continue through Day 21. If re-induction is required, a minimum 72-hour period is necessary between the dose of quizartinib on Day 21 and the administration of CPX-351 with re-induction.

If it is believed by the PI and/or sub-investigator that a patient with prolonged Grade ≥ 3 toxicity after the induction phase would be likely to experience additional toxicities during the consolidation phase, the patient could bypass the consolidation phase and proceed to a cellular intervention or the maintenance phase. Any patient with neutropenia or thrombocytopenia lasting ≥ 56 days from the initiation of CPX-351 will not receive consolidation and will instead proceed to the maintenance phase.

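### In consolidation Cycle 1 the Day 6 visit dates the quizartinib restart to Day 4, before its own QTcF check, and Appendix D both includes Day 21 in the dosing range and holds it

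*Combined protocol and SAP*

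**What the plan says.** **Start day.** At the Day 6 visit of consolidation Cycle 1 (6.4.2.2), the ECG bullet sets a QTcF condition of 470 msec or less and, if it is met, says to "resume quizartinib on Day 4". The next bullet of that visit reads "Quizartinib (begin daily until Day 21". Section 5.2.3 says "Quizartinib therapy (30 mg PO once daily) will start on Day 6 and continue through Day 21", and section 7.2 says "During the consolidation cycles(s), quizartinib begins on Day 6". The synopsis and the Appendix D table give Days 6 to 21. The matching Cycle 2 visit (6.4.2.6) carries the same ECG bullet but names no restart day.

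**Day 21.** Appendix D footnote b says "Begin quizartinib 30 mg PO once daily on Days 6-21 (hold quizartinib on Day 21". Footnote a does the same for induction, with Days 8 to 21. For re-induction, footnote a continues dosing through Day 21 but holds Day 21 only when the patient goes on to consolidation. Against this, 5.2.3 states that dosing "will start on Day 6 and continue through Day 21", the Appendix D table includes Day 21 in its ranges, and 5.2.2 requires at least 72 hours "between the dose of quizartinib on Day 21 and the administration of CPX-351 with re-induction".

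**The concern.** A result obtained on Day 6 cannot authorise a dose on Day 4. Quizartinib prolongs QTc in a dose-dependent way (1.5, 7.5.1), and QTcF prolongation is an adverse event of special interest (11.4.1.1), so the order of check and dose is operative safety text.

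The slip also cannot be dismissed as impossible to act on. An ECG is scheduled on consolidation Day 3, and a Day 4 start can meet the rule in 7.2 that quizartinib begins no earlier than 24 hours after the last CPX-351 dose, which is given on Day 3.

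The Day 21 wording raises a smaller question of the same kind: whether the last dose of the cycle falls on Day 21 or Day 20. Together, the two conflicts leave no single reference schedule for judging dosing compliance, exposure or protocol deviations.

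**Working it through.** No alpha, power or rate is involved. The check is a comparison of passages and a count of dosing days.

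**1. Consolidation start day, side by side**

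| Place | Start of quizartinib |
|---|---|
| Synopsis | Day 6 |
| 5.2.3 | Day 6 |
| 6.4.2.2 (Cycle 1, Day 6), ECG bullet | Day 4 |
| 6.4.2.2, next bullet | at the Day 6 visit |
| 6.4.2.6 (Cycle 2, Day 6), ECG bullet | no day named |
| 7.2 | Day 6 |
| Appendix D table and footnote b | Day 6 |

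Day 4 occurs once, in Cycle 1 only. Neither 6.4.2 nor the consolidation columns of Appendix D (Days 1, 3, 6, 14, 21 and 35) contain a Day 4 visit.

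**2. ECGs in the consolidation Cycle 1 visit list**

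- Day 3 (6.4.2.1): scheduled, no QTcF threshold, no quizartinib instruction.
- Day 6 (6.4.2.2): threshold of 470 msec, tied to quizartinib.
- Days 14 and 21 (6.4.2.3): scheduled, no threshold.

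Day 6 is the only ECG in that list with a threshold. A Day 4 start comes 6 − 4 = 2 days before it.

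**3. Day 21, side by side**

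| Place | Day 21 |
|---|---|
| 5.2.3 (consolidation) | dosed |
| 5.2.2 (washout before re-induction) | dose assumed given |
| Appendix D table | inside the dosing range |
| Footnote a, induction | inside the range and held |
| Footnote a, re-induction | dosed, but held if going to consolidation |
| Footnote b, consolidation | inside the range and held |

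The conflict lies within Appendix D, and within single footnote sentences, as well as between Appendix D and the body text.

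**4. Dosing days per cycle** (last day − first day + 1)

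| Cycle and literal reading | Day 21 given | Day 21 held |
|---|---|---|
| Consolidation, Day 6 start | 21 − 6 + 1 = 16 | 20 − 6 + 1 = 15 |
| Consolidation Cycle 1, Day 4 start | 21 − 4 + 1 = 18 | 20 − 4 + 1 = 17 |
| Induction, Day 8 start | 21 − 8 + 1 = 14 | 20 − 8 + 1 = 13 |
| Re-induction, Day 6 start | 21 − 6 + 1 = 16 | 20 − 6 + 1 = 15 |

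The Day 4 reading adds two days in consolidation Cycle 1. The Day 21 question moves each count by one.

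**The case against.** The best answer is that Day 4 is a visible slip. It sits inside a Day 6 visit, depends on that visit's result, is contradicted by the next bullet, has no visit of its own and is absent from Cycle 2. A site would more likely raise a query than dose early. Much of this stands: the instruction contradicts itself, so it is not a plain order to start early. It does not make the text harmless, because the Day 3 ECG and the 24-hour rule make Day 4 look workable.

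Three stronger readings are tempting, and the documents do not support them.

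- **Two extra days in every consolidation cycle.** Section 6.4.2.6 does not repeat Day 4, so the excess is confined to Cycle 1 and to patients who reach consolidation.
- **The sequence of FLT3 inhibitor after CPX-351 is broken.** Section 1.4 reports synergy when the inhibitor follows CPX-351, but not when it is given with or before it. Consolidation CPX-351 is given on Days 1 and 3, so Day 4 still follows it, and the rationale is not affected.
- **Dosing would begin with no ECG at all.** Section 7.2 asks for triplicate ECGs within 24 hours before initiation. It does not say whether this applies at the start of every cycle. If it does, a Day 4 start would still need its own ECG. What can be said is that Day 4 precedes the threshold check in the visit list.

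On Day 21, holding could mean stopping after that day's dose, which would agree with 5.2.2. The text does not say so, and the hold is unconditional for induction and consolidation but conditional for re-induction.

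**Conclusion.** The point holds as an internal inconsistency in operative dosing and QT-monitoring text, and it is minor in extent.

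- **Start day:** confined to consolidation Cycle 1. Read literally, it adds two dosing days (18 rather than 16 with Day 21 dosed, 17 rather than 15 with it held) and puts the start two days before the only ECG in that cycle's visit list with a QTcF threshold.
- **Day 21:** one dose is uncertain in induction (13 or 14 days) and in each consolidation cycle, and in re-induction only for patients who go on to consolidation.

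The counts assume one dose per calendar day with no interruption. How many sites would act on the Day 4 wording cannot be judged from the documents. Sample size and the primary test of response are not affected. No view is taken here on which start or stop day is right.

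**What to change.** 1. Reconcile 6.4.2.2 with the synopsis, 5.2.3, 6.4.2.6, 7.2 and Appendix D (table and footnote b), so that one start day and one ECG gate for it are stated throughout consolidation.
2. Reconcile the Day 21 hold in Appendix D footnotes a and b with 5.2.2, 5.2.3 and the Appendix D table. State explicitly whether a Day 21 dose is given in induction, re-induction and consolidation, and whether the condition attached to re-induction is intended.

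The clinical team decides the schedule. The change is to protocol wording only, with no effect on the sample size or the analysis. If patients have already entered consolidation, the start and stop days they actually followed should be recorded, so that exposure can be summarised against the reconciled schedule.
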